### 2.1.9.1 Experience with CHHI at George Washington University

A Phase 1 clinical trial of CHHI is currently underway at George Washington University (GWU) in Washington, DC, the same study site as will be used for the study described in this clinical protocol. This feasibility study (NCT01940757) is being conducted by [name] serving as study Principal Investigator. In it, 20 volunteers between the ages of 18 and 45 years who have no history of infection or exposure to hookworm were enrolled into 2 cohorts in a staggered fashion. In the first cohort volunteers received 25 *N. americanus* larvae whereas in the second cohort they received 50 larvae. All subjects (except 2 who were enrolled into a donor sub-study, see below) were cured of their infections by administering albendazole between 12 and 18 weeks post-infection.

In this study, adverse events have been mostly related to papulovesicular rash and pruritus at the site of larval application on the skin, and mild-to-moderate gastrointestinal symptoms most likely related to development of adult hookworms in the gastrointestinal tract. The skin reactions occurred immediately after application of larvae, have been graded by the study subjects as mild or moderate in most cases, and these have in some cases lasted for up to one month, sometimes with residual hyperpigmentation that gradually fades over time. Gastrointestinal symptoms consisting principally of mild to moderate abdominal bloating, flatulence and episodic nausea begin to occur approximately 4-6 weeks after infection. Skin reactions were more common in the 50 L3 cohort compared to the 25 L3 cohort, although there were no significant differences between the cohorts in incidence or severity of gastrointestinal complaints.

In the first cohort (25 L3), 3 of 10 subjects developed hookworm infections with eggs detectable in fecal samples by microscopy and PCR, whereas in the second (50 L3) cohort, 9 of 10 did. Mean egg counts, as estimated by the McMaster Method using all collected fecal samples, varied from 0 to 33 eggs per gram (epg) of feces in the 25 L3 cohort and from 0 to 133 epg in the 50 L3 cohort. Given the high rate of infection in the 50 L3 cohort, this will be the dose used in the Phase 2 clinical trial described in this protocol.

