### 11.2 Sample Size Considerations

Sample size considerations are based on the proportion of subjects with detectable hookworm eggs at any time, as measured by the saturated saline flotation technique. The primary analysis of the proportions will consist of comparing the proportion in each of the three *Na*-GST-1

intervention groups to the proportion in the placebo control group (group 4) using a one-sided Fisher exact test, for a total of three comparisons. The Holm-Bonferroni procedure will be used to control the familywise error rate at 0.05. Based on the results from the initial CHHI trial that was conducted at GWU (NCT01940757), we expect an infected proportion of 90% in group 4 (i.e., infectivity controls), and a proportion less than 20% in at least one of the intervention groups. At alpha=0.05/3, this yields a power of 87.7%. The power is 73.2% for an infection rate of 30% in intervention and 96.3% for an infection rate of 10%.

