- j. Percent change in IgG antibody levels from the day of CHHI to 1, 3, 5, 6, 7 and 9 months post-CHHI. Values will be reported with 95% confidence intervals.
- k. A longitudinal model will be built to describe the IgG levels over time. Using a longitudinal panel model, differences in antibody isotype levels by formulation of Na-GST-1 will be explored. This will be accomplished using Proc Mixed in SAS 9.3 so the analysis will take account of the correlation between measurements on the same subject.
- l. Logistic regression will be explored for the binary response of hookworm infection post-CHHI as a function of antibody response, and a Poisson regression of the event counts (i.e., infection) as a function of IgG antibody response. In these models, vaccination group will be a covariate, rather than just using the IgG responses.

**Exploratory Objective #1:** To assess the relationship between the functional capacity of vaccine-induced antibodies that neutralize the *in vitro* activity of native Na-GST-1 enzyme and responses to CHHI in healthy, hookworm-naïve adults.

*Exploratory Outcome #1 Measure:*

The following parameters will be evaluated for each formulation of Na-GST-1, in comparison to the saline placebo control:

1. The functional capacity of vaccine-induced antibodies to neutralize the *in vitro* activity of the native Na-GST-1 enzyme.

*Analysis Plan:*

- a. Percent inhibition of native enzyme activity will be displayed graphically for the various study groups at each time point.
- b. Three-way ANOVAs with Na-GST-1, CpG 10104, and AP 10-701 as factors and percent inhibition as the outcome will be estimated.
- c. A longitudinal model will be built to describe percent inhibition of native enzyme activity over time. Using a longitudinal panel model, differences in percent inhibition by formulation of Na-GST-1 will be explored. This will be accomplished using Proc Mixed in SAS 9.3, so the analysis will take account of the correlation between measurements on the same subject.

**Exploratory Objective #2:** To compare the impact of vaccination with Na-GST-1/Alhydrogel® delivered with or without AP 10-701 or CpG 10104 on levels of hookworm DNA as detected by real-time PCR in healthy, hookworm-naïve adults challenged with CHHI.

*Exploratory Outcome #2 Measure:*

The following parameters will be evaluated for each formulation of Na-GST-1, in comparison to the saline placebo control:

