### 3. DATA ANALYSIS CONSIDERATIONS

#### 3.1 Determination of Sample Size

Sample size considerations are based on the proportion of subjects with detectable hookworm eggs at any time, as measured by the saturated saline flotation technique. The primary analysis will consist of comparing the proportion of subjects in each of the three *Na*-GST-1 vaccination groups (groups 1, 2 and 3) to the proportion of subjects in the placebo control group (group 4) using a two-sided Fisher exact test, for a total of three comparisons. Targeting a rate of 90% subject hookworm infection as observed in the 50 *Na*-L3 dose cohort and a greater than 80% rate of protection in at least one of 3 vaccination groups (e.g., different doses or adjuvant formulations) compared to controls that did not receive the hookworm vaccine, a sample size of 48 (12 per group) would be sufficient to demonstrate the efficacy of a prophylactic hookworm vaccine such as *Na*-GST-1 or *Na*-APR-1, with alpha ~ 0.1 and power of at least 80% [[name] et al, OFID, April 2018].

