A longitudinal model will be built to describe the IgG levels over time. Using a longitudinal panel model, differences in antibody isotype levels by vaccination groups and placebo will be explored. The analysis will take account of the correlation between measurements on the same subject. A mixed model repeated measure (MMRM) will be fitted with IgG levels as the dependent variable and vaccination groups and placebo, visits and interaction between groups and visits as independent variables. the estimated geometric means Standard Error and geometric means difference from the model, 2-sided *p*-value and 95% CI for vaccination groups and placebo will be constructed.

Logistic regression will be explored for the binary response of hookworm infection post-CHHI as a function of antibody response. Dependant variable will be the hookworm infection status (Positive/Negative) and independent variable will be the IgG responses and vaccination groups and placebo. Estimated number of subjects, Standard Error and odds ratio from the model, 2-sided *p*-value and Wald 95% CI for vaccination groups and placebo will be constructed.

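### In the model relating IgG to infection, group odds ratios and their Wald intervals will often have no finite value, and the visit supplying IgG is not fixed

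*SAP*

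**What the plan says.** Secondary objective 2 in both documents is to relate the antibody response to infection after challenge. SAP 5.7.4.2 addresses it with a logistic regression that is to be explored. The outcome is infection status, and the "independent variable will be the IgG responses and vaccination groups and placebo". The requested output is an odds ratio, a standard error, a two-sided p-value and a "Wald 95% CI for vaccination groups and placebo will be constructed". As worded, the interval is for the group terms; no IgG odds ratio or interval is clearly requested.

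Protocol 11.4 (Secondary Outcomes #2 and #3, item l) has the same structure: "In these models, vaccination group will be a covariate, rather than just using the IgG responses". It adds a Poisson regression on IgG, which SAP 5.7.4.2 does not carry.

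On size and expected rates, SAP 3.1 says "a sample size of 48 (12 per group) would be sufficient". Protocol 11.2 says "we expect an infected proportion of 90% in group 4 (i.e., infectivity controls" and expects "a proportion less than 20% in at least one of the intervention groups".

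The SAP's only rule for a failed computation, in section 5.1, is to show the value as not computable. No penalised, exact or profile-likelihood method is named.

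**The concern.** A group in which everyone or no one is infected has no finite maximum-likelihood log odds ratio. The fit drifts until the software stops, the standard error grows without limit, and the Wald interval means nothing. With 12 per group and rates expected near 90% and 20%, such groups are likely, and they affect exactly the quantities that SAP 5.7.4.2 asks to be printed. If placebo is the reference group and is 12/12, all three vaccine-versus-placebo odds ratios fail together.

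The second gap is the predictor. Neither document says which visit's IgG, or which scale, enters this model. IgG drawn after challenge may partly reflect infection, and an association with it could not be read as a correlate of protection.

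**Working it through.** **Inputs.** 12 per group and four groups (SAP 3.1). Placebo infection 90% (Protocol 11.2), resting on the feasibility study's 50-larvae cohort: "whereas in the second (50 L3) cohort, 9 of 10 did" (Protocol 2.1.9.1). At least one vaccine group below 20% (Protocol 11.2). The documents give no rates for the other vaccine groups, no IgG variance and no dropout rate, so these are assumed below.

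**The plan's own figure.** Protocol 11.2 bases power on comparing each vaccine group with placebo "using a one-sided Fisher exact test, for a total of three comparisons", at alpha 0.05/3. Full enumeration with 12 versus 12 and 90% on placebo gives 88.8%, 74.1% and 97.5% at vaccine-group rates of 20%, 30% and 10%. The protocol states 87.7%, 73.2% and 96.3%. All agree within 2 points, so the inputs are read correctly.

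**Placebo alone.** P(12/12 infected) = 0.9^12 = 28.2%. At a true rate of 0.80 it is 6.9%, and at 0.95 it is 54.0%. With 11 or 10 subjects at 90% it is 31.4% or 34.9%.

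**Any group.** A group with true rate p has both outcomes with probability 1 − p^12 − (1−p)^12:
- 0.7176 at 90% or 10%
- 0.9313 at 80% or 20%
- 0.9862 at 70% or 30%
- 0.9995 at 50%

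P(at least one group 0/12 or 12/12) is one minus the product over the four groups. For 20/20/20/90 it is 1 − 0.9313³ × 0.7176 = 42.0%.

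| Rates, Groups 1/2/3/placebo (%) | P(at least one group 0/12 or 12/12) |
|---|---|
| 50/20/20/90 | 37.8% |
| 20/20/20/90 | 42.0% |
| 80/30/10/90 | 52.7% |
| 90/20/20/90 | 55.3% |
| 90/90/90/90 | 73.5% |

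Two other mixes show the dependence on the assumed rates: 70/50/20/90 gives 34.1%, and 90/90/20/90 gives 65.6%. With 10 per group (an assumed loss; leavers are not replaced), the table's range of 38 to 73.5% becomes 48 to 82%. At a placebo rate of 80% with all vaccine groups at 50% it is only 7%.

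**The IgG coefficient.** In simulation (2,000 trials per scenario; standardised IgG, near-constant on placebo), almost all separation came from 0/12 or 12/12 groups. The IgG coefficient was non-finite in 0 to 3% of trials for odds ratios per SD from 1 to 0.25, and in 0.3 to 8% at 0.1. A further run of the five tabulated scenarios (1,000 trials each; infection unrelated to IgG within group, placebo IgG exactly constant) gave 0.0, 0.0, 0.2, 0.3 and 4.1%. The 4.1% is the all-90% case, where all three vaccine groups are 12/12 with probability 0.2824³ = 2.3% and nothing is left to estimate the slope from.

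In scenarios with a vaccine effect, the IgG Wald interval covered the true value in 95 to 98% of trials. Power for IgG was 15 to 36% at an odds ratio of 0.5 per SD and 36 to 82% at 0.25.

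**An illustration.** Take placebo 12/12 and vaccine groups 8/12, 6/12 and 2/12. As maximum-likelihood iterations rose from 8 to 25, the Group 3 versus placebo log odds ratio went from −10.35 to −27.35 and its standard error from 13.1 to 64,393. The IgG coefficient stayed at −0.776 (SE 0.475), with or without placebo. Firth gave −4.69 (SE 1.68) for Group 3 and −0.64 (SE 0.44) for IgG. Across six scenarios of 800 trials each, every Firth fit was finite.

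**IgG visits.** The visit lists in Protocol 7.2 to 7.4 schedule antibody blood on 16 days: 0, 14, 56, 70, 112, 126, 140, 147, 154, 175, 189, 231, 280, 297, 320 and 380. The last nine follow larval application on Day 140. The secondary IgG endpoint (SAP 4.2) includes months 2 to 10 after dose 3, all after challenge. Protocol 11.4 fixes Day 126 for the pairwise IgG comparisons (item f) and for memory B cells, but no visit is fixed for this model.

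**The case against.** A reader might infer that, because the model so often fails to converge, secondary objective 2 would go unanswered. The documents do not support that. The objective concerns the relation of IgG to infection, which is the IgG coefficient. A group with only one outcome has its own indicator absorb the problem, and the slope is still estimated from the groups with both outcomes. Placebo subjects near the assay floor say almost nothing about the slope, so a 12/12 placebo group cannot harm it. The main limit on the IgG estimate is 48 subjects, which penalisation does not cure.

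Other points also stand. Both documents label the model exploratory. Vaccine-versus-placebo infection is already tested by Fisher's exact test (SAP 5.7.4.1), which empty cells do not disturb, and time to patency by log-rank, so no primary conclusion rests on these odds ratios. The highest figure, 73.5%, contradicts the plan's expectation of at least one vaccine group below 20%. The 90% rate comes from ten subjects.

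What the objection does not remove: the quantities that clearly fail are those the SAP asks for, the surviving IgG estimate is not clearly requested, showing a value as not computable is a display rule rather than a method, and post-challenge IgG is not excluded.

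**Conclusion.** The concern holds for the group terms and for the undefined IgG predictor. Some group odds ratio and its Wald interval will lack a finite value in about 38 to 55% of trials under the four tabulated vaccine-effect scenarios, and in 73.5% if no formulation works and all groups are at 90%. Placebo alone contributes 28%. These figures rest on the 90% placebo rate, 12 evaluable subjects per group, and assumed vaccine-group rates beyond the single one the protocol anticipates.

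The IgG coefficient stays finite in about 97% or more of simulated trials (96% in the all-90% run with constant placebo IgG), and in about 92% or more if the IgG effect is extreme. Those figures rest on assumed IgG spread and effect size. Secondary objective 2 would therefore be answered imprecisely, not left unanswered. The missing IgG visit needs no probability assumption and matters at least as much, because it decides whether the estimate can be read as a correlate of protection.

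**What to change.** In SAP 5.7.4.2:

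- Replace the maximum-likelihood fit and Wald intervals with Firth penalised-likelihood logistic regression and profile-likelihood 95% intervals, keeping all four groups and naming placebo as the reference. Dropping placebo is unnecessary: it left the IgG estimate unchanged in the illustration.
- State that the IgG odds ratio and its interval are the correlate estimate to be reported.
- Define the predictor as log IgG from one named pre-challenge visit. Day 126 matches the protocol's other single-visit comparisons. Day 140 also serves, since Protocol 7.3 lists that blood draw before larval application. Neither needs a new sample.

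The cost is SAP wording and a model option. Estimates shrink slightly towards no effect, and power for IgG may fall somewhat: in the simulations, Firth with a Wald-type test had 11 to 26% power at an odds ratio of 0.5 per SD, against 15 to 36% for maximum likelihood.

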#### 5.7.5 Safety Analysis

All safety assessments, including adverse events, solicited and unsolicited adverse events during the post-vaccination phase and post-CHHI phase, clinical laboratory test results, vital signs, (blood pressure [mmHg], heart rate [bpm], and oral temperature [Degrees Celsius]), abnormal physical examination

findings will be listed by subject and tabulated when applicable. The analysis will be performed on the Safety Population.

#### 5.7.5.1 Adverse Events

Adverse Events (AEs) will be coded using the Medical Dictionary of Regulatory Activities (MedDRA version 23.0 or higher) AE coding system for purpose of summary tables.

An AE is any that is new in onset or was increased in severity following the first dose of study product, up to and including the last procedure of the study (i.e., Follow-up phone call).

Summary tables of the following AEs will be provided:

- An overview of AE summary will be presented by Vaccine Group and it will include number and percentages of subjects who had at least one AE, who had at least one SAE, who had at least one vaccine-related AE, who had at least one vaccine -related serious AE, who had at least one AESI, subjects who had at least one vaccine-related AESI and who had at least one AE leading to study discontinuation will be presented.
- A summary of the frequency (number and percentage of subjects) of AEs by Vaccine group will be presented by system organ class, preferred term.
- Similar summary results will be generated for AEs by severity (mild, moderate, severe) and by relationship (Definitely, Probably, Possibly, Unlikely and not related) to study product. AEs and SAEs associated with study discontinuation will be include in by subject data listings.
- A summary of the frequency (number and percentage of subjects) of SAEs by Vaccine Group will be presented by system organ class, and preferred term.
- A summary of the frequency (number and percentage of subjects) of vaccine related SAEs by Vaccine Group will be presented by system organ class, and preferred term.
- A summary of the frequency (number and percentage of subjects) of clinical safety laboratory AEs by Vaccine Group will be presented by system organ class, and preferred term.
- A summary of the frequency (number and percentage of subjects) of new-onset chronic medical conditions through approximately 10 months after the third study vaccination by Vaccine Group will be presented by system organ class, and preferred term.
- Similarly, a separate table will be provided for Adverse Events of Special Interest through approximately 10 months after the third study vaccination using number and percentage of subjects by Vaccine Group, and will be presented by system organ class, and preferred term.
- Additionally, the proportion of subjects with at least one injection site AE and frequency of AEs grouped by SOC term will be compared by *Na-GST-1* vaccine formulation and placebo. The null hypotheses that the Adverse event type and number of adverse events is the same across all vaccination groups and placebo. 2-sided *p*-values will be obtained from the Fisher's exact test.

All AEs during the study will be summarized for the respective vaccination. A subject experiencing the same AE multiple times will be counted only once for that preferred term. Similarly, if a subject experience multiple AEs (preferred terms) within the same system organ class then that subject will be

counted only once for that system organ class. When summarizing by severity, only event with highest severity will be counted. All AEs will be listed in chronological order of the events occurred.

Individual subject listings containing all information pertaining to adverse events noted during the study will be presented by Vaccine Group, subject, verbatim and preferred terms, system organ class, start date, stop date, maximum severity, outcome, action taken and study vaccine relatedness.

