Recruitment and enrollment into the study will occur on an ongoing basis, with each group being recruited and vaccinated in sequence.

48 subjects will be enrolled into 4 groups of 12:

[figure not shown]
Subjects will be enrolled sequentially and upon enrollment will be randomized to one of the following IP assignments in a double-blind fashion:

- Group 1 IP allocation (n=12 subjects):
  - 12 subjects will receive 100 $\mu$ g Na-GST-1/Alhydrogel® delivered by IM injection in the deltoid muscle.
- Group 2 IP allocation (n=12):
  - 12 subjects will receive Na-GST-1/Alhydrogel® plus 500 $\mu$ g CpG 10104 delivered by IM injection in the deltoid muscle.
- Group 3 IP allocation (n=12):

- 12 subjects will receive Na-GST-1/Alhydrogel® plus 5µg AP 10-701 delivered by IM injection in the deltoid muscle.
- Group 4 IP allocation (n=12):
  - 12 subjects will receive sterile saline delivered by IM injection in the deltoid muscle

**Estimated Time to Complete Enrollment:** 6 months

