#### Safety

The following parameters will be evaluated for each formulation of Na-GST-1, in comparison to the saline placebo control:

1. Frequency of solicited injection site and systemic reactogenicity, graded by severity, on the day of each study vaccination through 14 days after each study vaccination.
2. Frequency of solicited adverse events, graded by severity, on the day of CHHI through study Day 280.
3. Frequency of study vaccine-related Serious Adverse Events from the time of the first study vaccination through approximately 10 months after the last study vaccination.
4. Frequency of clinical safety laboratory adverse events.
5. Frequency of unsolicited adverse events, graded by severity, from the time of each study vaccination through approximately 1 month after each study vaccination; and from the time of CHHI through treatment with albendazole (Day 297).
6. Frequency of new-onset chronic medical conditions through approximately 10 months after the third study vaccination.
7. Frequency of Adverse Events of Special Interest through approximately 10 months after the third study vaccination.

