## 9 ASSESSMENT OF SAFETY

### 9.1 Specification of Safety Parameters

Safety will be assessed by the frequency and severity of:

1. Study product (vaccine or CHHI)-related serious adverse events occurring from the time of the first study vaccination through approximately 10 months after the last study vaccination.
2. Study vaccine-related solicited Adverse Events – reactogenicity events occurring on the day of each study vaccination through 14 days after each study vaccination:
  - a) Injection site reactions including erythema (redness), induration (hardness)/swelling, pain, and tenderness.
  - b) Systemic reactions including fever, myalgia (body aches/muscular pain exclusive of the injection site), arthralgia (joint pain exclusive of the injection site), headache, nausea, and vomiting.
3. CHHI-related solicited adverse events – reactogenicity events occurring on the day of CHHI through study Day 280 (time of treatment with first dose of albendazole):
  - a) Application site reactions including pruritus, rash, induration (hardness)/swelling, pain, and tenderness.
  - b) Gastrointestinal reactions including abdominal pain, abdominal bloating, flatulence, nausea, vomiting, and diarrhea.
  - c) Respiratory reactions (possibly due to migration of larvae through the lungs) including cough and sore throat.
4. Clinical safety laboratory adverse events occurring throughout the study. Parameters to be evaluated include WBC, ANC, absolute eosinophil count, hemoglobin concentration, and platelet count; ALT; creatinine; rheumatoid factor; and, anti-ds DNA antibodies.
5. Unsolicited Adverse Events – non-serious adverse events occurring from the time of each study vaccination through approximately 28 days after each vaccination and from study Day 140 (day of CHHI) through Day 297.
6. New-onset chronic medical conditions occurring from the time of the first study vaccination through approximately 10 months after the last study vaccination.
7. Adverse Events of Special Interest occurring from the time of the first study vaccination through approximately 10 months after the last study vaccination.

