### **5.7.4 Primary and Secondary Analysis**

#### **5.7.4.1 Primary Endpoint Analysis**

The primary efficacy endpoint analysis of proportion of subjects with detectable hookworm eggs in fecal samples, at any time point post-CHHI, will be summarized using frequency counts and percentages as a descriptive measure at time points post-CHHI for all vaccination groups.

Along with the summaries for any time points post-CHHI, the proportion of subjects with detectable hookworm eggs in fecal samples will be summarized as a descriptive measure by study group at each time point.

The proportion of subjects with detectable hookworm eggs in each of the vaccination groups (Groups 1, 2 and 3) will be compared to the proportion of subjects in the placebo control group (Group 4) using a two-sided Fisher exact test. The p-values for the pairwise comparison of proportions of subjects in the vaccination groups (Group 1, 2 and 3) and placebo group (Group 4) will be reported. No adjustments for multiple comparisons will be made and therefore, the reported p-values will have to be interpreted with caution.

The proportion of subjects with at least one injection site AE and the frequency of the AE grouped by PT will be compared by *Na*-GST-1 vaccine formulation and placebo. The null hypotheses that the type and number of adverse events is the same across all groups will be tested using Fisher's exact test.

Laboratory results (haematological and clinical chemistry) will be descriptively examined and any clinically significant values for individuals will be reported.

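### The SAP's Fisher tests of adverse events by preferred term and by SOC merge the vaccination and larval-challenge phases, which dilutes the vaccine-versus-saline safety comparison

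*SAP*

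**What the plan says.** **The tests.** SAP 5.7.4.1 states that "the frequency of the AE grouped by PT will be compared by" vaccine formulation and placebo, with Fisher's exact test. SAP 5.7.5.1 repeats the comparison by SOC, two-sided. Both sections also test the proportion of subjects with at least one injection-site AE.

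**The window and the count.** SAP 5.7.5.1 defines an AE as anything new or worse after the first dose, "up to and including the last procedure of the study". On counting it says "A subject experiencing the same AE multiple times will be counted only once for that preferred term", and it applies the same rule to each SOC. The sentence just before ties the summary of all AEs in the study to the respective vaccination. It gives no dates and does not say where post-challenge events belong.

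**The outcomes served.** Protocol 3.2.1 and SAP 4.1 use separate windows: solicited events for 14 days after each dose and from challenge to Day 280; unsolicited events for about one month after each dose and from challenge to Day 297.

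**The overlap.** The vaccination-phase solicited list in Protocol 9.1 includes nausea and vomiting. The challenge list adds "Gastrointestinal reactions including abdominal pain, abdominal bloating, flatulence, nausea, vomiting, and diarrhea".

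**Attribution.** Protocol 9.2.1 grades every AE for relationship to vaccine or to CHHI, and Protocol 9.1 counts SAEs related to either. Protocol 3.2.1 outcome 3 is narrower: "Frequency of study vaccine-related Serious Adverse Events from the time of the first study vaccination". The relatedness rows in the SAP overview are vaccine-related only.

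**The concern.** Primary Objective 2 is the safety and reactogenicity of three vaccine formulations, judged against saline. Saline is a clean reference only until Day 140, when all four arms are exposed to larvae. After that a saline subject can acquire nausea from the challenge. Under a once-per-study count that subject scores the same as a vaccinee who was nauseated after each dose. For a shared term, the challenge adds affected subjects to both arms and narrows the gap that the vaccine caused.

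The SOC test is more exposed than the PT test. Protocol 9.1 groups all six challenge symptoms above as gastrointestinal, so a vaccinee's nausea may be merged with any of them. For systemic events, these PT and SOC tests are the only between-arm AE tests that the SAP plans. SAP section 1 says that safety results will feed decisions on later studies.

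**Working it through.** **Inputs from the documents**
- Arm size: 12 (Protocol summary: "48 subjects will be enrolled into 4 groups of 12").
- Test: Fisher exact, two-sided (SAP 5.7.5.1).
- Infection rates for planning: "we expect an infected proportion of 90% in group 4" and below 20% in at least one vaccine group (Protocol 11.2).

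**Inputs that are assumptions.** The documents give no AE rate by phase and arm, and no power for any safety test. All AE rates below are assumed. The two phases are taken as independent, each comparison is one vaccine arm against saline at 0.05, and dropout is zero.

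**Check of the method.** Protocol 11.2 compares the "intervention groups to the proportion in the placebo control group (group 4) using a one-sided Fisher exact test", at alpha 0.05/3. Exact enumeration of two Binomial(12, p) arms, at 90% infected in controls, gives:

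| Infected in vaccine group | Protocol power | Enumeration |
|---|---|---|
| 20% | 87.7% | 88.8% |
| 30% | 73.2% | 74.1% |
| 10% | 96.3% | 97.5% |

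Each is within about 1.2 points, which is close enough to use the method for the safety tests.

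**Dilution with the same challenge rate in every arm.** Let v be the risk after vaccination and c the risk after challenge. The whole-study risk is 1 − (1 − v)(1 − c). Take v = 60% for vaccine and 5% for saline. At c = 50%, vaccine is 1 − 0.40 × 0.50 = 80.0% and saline is 1 − 0.95 × 0.50 = 52.5%.

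| c | Vaccine | Saline | Power |
|---|---|---|---|
| vaccination phase only | 60.0% | 5.0% | 78.4% |
| 20% | 68.0% | 24.0% | 47.5% |
| 30% | 72.0% | 33.5% | 35.9% |
| 50% | 80.0% | 52.5% | 17.4% |
| 70% | 88.0% | 71.5% | 6.4% |

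A smaller vaccine effect, 50% against 10%, starts at 42.5% power and falls to 9.2% at c = 50%.

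**A SOC that holds both injection-site and larval-site reactions.** This applies only if the coding puts both in one SOC. Assume injection-site reactions in 75% of vaccinees and 15% of saline subjects, and larval-site reactions in 80% to 90% of both arms. Power falls from 81.4% to 2.2% at 80% and 0.2% at 90%.

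**Can the order reverse?** Let the challenge risk depend on infection: c = (infected share × rate if infected) + (uninfected share × rate if not). Use 20% infected in the vaccine arm, 90% in saline, and 40% against 10% after vaccination.
- Rates of 60% if infected and 5% if not: c = 0.2 × 0.60 + 0.8 × 0.05 = 16.0% for vaccine and 0.9 × 0.60 + 0.1 × 0.05 = 54.5% for saline. Whole-study risks are 1 − 0.60 × 0.84 = 49.6% and 1 − 0.90 × 0.455 = 59.1%. The order reverses.
- Rates of 40% and 5%: c = 12.0% and 36.5%. Whole-study risks are 47.2% and 42.9%. It does not reverse.
- Rates of 50% whether infected or not: 70% and 55%. It does not reverse.

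**The case against.** **The vaccination-phase signal can still be seen.** SAP 5.7.5.2 tabulates post-vaccination events by severity and group in the Safety Population, with solicited events by day and by dose. SAP 5.7.5.3 does the same after challenge. This stands, and it limits the harm: a careful reader of the report could find the signal. The tables carry no between-arm test, however. The post-challenge table is also restricted to the Per Protocol Population, although SAP 5.7.5 assigns safety analysis to the Safety Population.

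**A formal test without the mixing exists.** The injection-site AE test is vaccine-specific and is largely unaffected, provided that larval-site events are not coded as injection-site. So it would be wrong to infer that the plan has no sound formal safety test. That test does not cover systemic reactions.

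**The overlap is limited.** Only nausea and vomiting are on both solicited lists; fever, headache, myalgia and arthralgia are not solicited after challenge. At PT level this confines the problem among solicited events to two terms. At SOC level it is wider.

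**The per-vaccination sentence could be read as a split.** It sets no window and does not place post-challenge events, so two programmers could produce different tables from it.

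**The overview is not confined to vaccine-related events.** It also counts any AE, any SAE and any AESI. What it lacks is a row for relatedness to CHHI.

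**The tests are supportive.** With 12 per arm, in a trial meant to inform a larger one, they are not decisive, and Protocol 11.4 sets no phase for its own AE tests either. This lowers the stakes but does not make the count match the outcomes.

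**Conclusion.** The point holds as dilution. The PT and SOC tests do not respect the windows of the primary safety outcomes. For shared terms they can lose most of their power even when challenge symptoms are equally common in every arm: from 78% to between 48% and 6% under the assumed rates. The size depends on those rates. The direction needs only that some subjects have the same term after challenge.

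A reader might go further and infer that a reactogenic but protective formulation would look safer than saline. The documents do not support this. It requires challenge symptoms to depend strongly on infection, and it disappears under the milder assumptions above. Protocol 2.1.9.1 reports no significant difference in gastrointestinal complaints between a cohort with 3 of 10 infected and one with 9 of 10. Those cohorts are small and received different larval doses, so they do not exclude a link, but they show none. Reversal is a possibility under chosen inputs; loss of signal is the finding.

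**What to change.** In SAP 5.7.4.1 and 5.7.5.1:
- Run the PT and SOC tables and Fisher tests separately for (a) the vaccination phase, with onset from dose 1 to before larval application and within 28 days of a dose, and (b) the CHHI phase, with onset from larval application to Day 297.
- Count each term once per subject per phase.
- Base the vaccine-versus-saline safety comparison on (a).
- Replace or define the wording on the respective vaccination.
- Add CHHI-relatedness, already collected under Protocol 9.2.1, beside the vaccine-relatedness rows. Reconcile outcome 3 in Protocol 3.2.1 with Protocol 9.1.

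The cost is SAP wording, one aligned outcome definition, and one extra set of tables and tests. No new data are needed.
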